Aim 1: Examine the association between exposure to “natural” or “organic” cigarette descriptors and: 1) health risk expectancies (e.g., chemical content); 2) subjective effects of smoking (e.g., chemical taste); 3) smoking topography (e.g., total puff volume); and 4) biomarkers of exposure (e.g., salivary aldehydes).

H_{1.1}: More participants will rate cigarettes in the “natural” and “organic” conditions as having fewer chemicals relative to cigarettes in the “conventional” condition.

H_{1.2}: Participants’ average ratings of the “chemical aftertaste” of the cigarettes in the “natural” and “organic” conditions will be higher (e.g., closer towards the “less chemical aftertaste” side of the scale) relative to their average ratings of the cigarette in the “conventional” condition.

H_{1.3}: Total puff volume will be higher in the “natural” and “organic” conditions than the “conventional” condition.

H_{1.4}: Change in salivary aldehyde concentrations pre/post administration of the study cigarette(s) will be higher in the “natural” and “organic” conditions than the “conventional” condition.

Aim 2: Examine whether the relationships in Aim 1 differ by preference for a “natural/organic” cigarette brand (NAS smokers vs. non-NAS smokers).

H_{2.1}: Compared to non-NAS smokers, more NAS smokers will rate the “natural” and “organic” conditions as having fewer chemicals relative to their ratings in the “conventional” condition, but not relative to their own brand condition.

H_{2.2}: Compared to non-NAS smokers, NAS smokers’ average ratings of the “chemical aftertaste” of the cigarettes in the “natural” and “organic” conditions will be higher (e.g., closer towards the “less chemical aftertaste” side of the scale) relative to their average ratings of the cigarette in the “conventional” condition, but not relative to their own brand condition

H_{2.3}: NAS smokers’ total puff volume will be lower in the “conventional” condition than the “natural,” “organic,” and own brand conditions.

H_{2.4}: NAS smokers’ change in salivary aldehyde concentrations pre/post study cigarette(s) administration will be lower in the “conventional” condition than the “natural,” “organic,” and own brand conditions.

Aim 3: Examine if relationships in Aim 1 differ by gender.

H_{3.1}: A greater proportion of women than men will rate the cigarettes in the “natural” and “organic” conditions as having fewer chemicals relative to cigarettes in the “conventional” condition.

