Sample size calculations were performed using GLIMMMPSE Version 3.⁴³ Though a Bayesian model averaging approach will be used, sample size calculations using a non-Bayesian approach are applicable here because they correspond to the model that is believed to be most likely true *a priori*, and also because we plan to use uninformative priors on the parameters in the model, which makes our analyses comparable to the non-Bayesian approach that is used for sample size calculations. As we do not have pilot data to inform our sample size calculations for the NAS/non-NAS group, our sample size calculations are based on the group means by gender that were observed in the pilot study on “total puffs” and a standard deviation of 5.5.³¹ Given NAS smokers’ preexisting misperceptions about natural/organic cigarettes, we anticipate that group means will be more extreme in the NAS/non-NAS group.⁴⁴ Thus, the minimum sample size required for Aim 3 analyses should be sufficient to address the Aim 2 analyses. Assuming an intraclass correlation between repeated measurements of 0.5, 40 total subjects are needed to detect a significant interaction between gender and condition (natural/organic vs conventional/own brand) at 90% power and a significance level of 5%, while 99% power requires 68 subjects. Since these assumptions use information based on only 22 subjects in the pilot study, sample size calculations were also performed with an effect size 50% smaller and a

covariance matrix 50% larger than assumed: under these conditions, 90% power is achieved with 228 total subjects. Fewer subjects are needed to detect differences hypothesized in Aim 1 at each given power; for example, under the smallest effect size observed in the topography pilot data (which assumes a mean difference of 120ml with standard deviation 165ml), 120 subjects are needed to achieve 90% power under an effect size that is 50% smaller and covariance matrix that is 50% larger than assumed. Thus, we will enroll 125 participants per cigarette type (250 total, though we have budgeted for up to 300 participants to account for loss to follow up) to ensure at least 228 participants complete the full study. Our proposed sample size is adequate to detect a similar topography effect size to our pilot study, examine moderation by NAS preference and gender, and allow for adjustments to the significance level due to multiple comparisons.

Statistical analyses

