95% credible intervals will be estimated for the difference in effects between 9) 4. - 2. and 8. - 6., 10) 3. - 2. and 7. - 6., 11) 4. - 1. - (2. - 1.) and 8. - 5. - (6. - 5.), and 12) 3. - 1. - (2. - 1.) and 7. - 5. - (6. - 5.). If the credible interval in 9) / 10) does not contain 0, then there is evidence that men smokers mean outcome under the organic / natural condition relative to the convention condition differs from the women smokers mean outcome under the organic / natural condition relative to the convention condition, which would provide evidence against the null hypothesis in H(3.1) and H(3.2). If the credible interval in 11) / 12) does not contain 0, then there is evidence that men smokers mean outcome difference between the organic / natural condition relative to the own brand condition and convention condition relative to own brand condition differs from the women smokers mean outcome difference between the organic / natural condition relative to the own brand condition and convention condition relative to own brand condition, which would provide evidence against the null hypothesis in H(3.3) and H(3.4) (assuming the direction of the difference is not opposite the hypothesized direction).

Biomarker analyses

Previous work, including our preliminary biosample analyses, demonstrate that short exposures similar to our 15 min ad lib bout increase exposure biomarkers like saliva nicotine (>200-fold) and aldehydes (2-10-fold).^{54,55} Participants' saliva samples (before and after tobacco use sessions) will be characterized for nicotine and aldehyde concentrations and compared across descriptor conditions.

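### The 90% moderation power is stated for a contrast that groups own brand with conventional, a grouping that no planned Aim 2 or Aim 3 test uses

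*Combined protocol and SAP*

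**What the plan says.** The Sample size calculations section bases moderation power on pilot data by gender: "our sample size calculations are based on the group means by gender that were observed in the pilot study on" total puffs, with "a standard deviation of 5.5". The powered interaction is described as one to "detect a significant interaction between gender and condition (natural/organic vs conventional/own brand) at 90% power". Three totals follow: 40 for 90% power, 68 for 99% power, and 228 for 90% power when the effect is 50% smaller and the covariance matrix 50% larger. The 228 is the completer target behind enrolling 250. The section then extends the result: "Thus, the minimum sample size required for Aim 3 analyses should be sufficient to address the Aim 2 analyses", because NAS smokers' means are expected to be more extreme.

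The analysis sections treat own brand differently:

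- Statistical analyses: the condition effect that may vary by gender or NAS status covers conventional, organic and natural. Own brand has its own term. Only natural and organic may be combined.
- Hypothesis testing, Aim 3: "95% credible intervals will be estimated for the difference in effects between 9) 4. - 2. and 8. - 6", that is, organic minus conventional in men against the same difference in women. Item 10 does this for natural.
- Hypothesis testing, Aim 2: H2.1 and H2.2 compare NAS with non-NAS smokers on each descriptor minus conventional and, separately, on each descriptor minus own brand. H2.3 and H2.4 use the same pairs within NAS smokers only.
- Aims & Hypotheses, H2.3: NAS smokers' "total puff volume will be lower in the" conventional condition than in the natural, organic and own brand conditions.

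**The concern.** Power belongs to a specific contrast. If the powered contrast averages two conditions on each side and the tested one does not, the tested one has a larger variance, and 90% does not carry over without further argument. Grouping conventional with own brand also assumes that the two behave alike. Aim 2 hypothesises the opposite for NAS smokers, so larger NAS differences alone cannot justify reusing the Aim 3 number; the pattern of means differs, not only its size.

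The stake is how a null result is read. For Aim 2, the Hypothesis testing section takes an interval that contains 0 as evidence for the null. If the tested interactions have less power than stated, a missed moderation effect would be reported as no difference.

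**Working it through.** **Inputs.** From Sample size calculations: SD 5.5 puffs; "Assuming an intraclass correlation between repeated measurements of 0.5, 40 total subjects are needed to detect a significant interaction between gender and condition"; "at 90% power and a significance level of 5%, while 99% power requires 68 subjects"; and 228 for the pessimistic scenario (effect × 0.5, covariance × 1.5). From Recruitment: half women as a goal. Assumed: two-sided test, equal groups, compound symmetry. Not given: the gender-by-condition means. The effect is therefore back-solved and is an assumption.

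**Formulas.** A within-person contrast with weights w has variance V = σ²(1 − ρ)Σw², with σ²(1 − ρ) = 30.25 × 0.5 = 15.125.

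- (natural + organic)/2 − (conventional + own brand)/2: Σw² = 4 × ¼ = 1, V = 15.125
- (natural + organic)/2 − conventional: Σw² = ¼ + ¼ + 1 = 1.5, V = 22.69
- organic (or natural) − conventional: Σw² = 1 + 1 = 2, V = 30.25

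Comparing the contrast δ between two equal groups, N in total, gives noncentrality δ/√(4V/N) on N − 2 df.

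**The plan's figures.** Take the two-versus-two contrast and solve for 90% power at 228 in the pessimistic scenario: δ = 4.11 puffs, halved to 2.054, with variance 1.5 × 15.125 = 22.69. Noncentrality is 2.054/√(4 × 22.69/228) = 2.054/0.631 = 3.26, power 90%. The same δ, unhalved and with V = 15.125, returns 40 for 90% and 68 for 99%. So 40, 68 and 228 agree with each other. The 40 itself cannot be checked without the means.

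**Tested contrasts, same δ, pessimistic scenario.** This step assumes equal conventional and own-brand means.

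- Combined natural/organic against conventional: 3.26/√1.5 = 2.66, power 75% at 228. At 250, multiply by √(250/228) = 1.047: 2.78, power 79%. N for 90% is 228 × 1.5 = 342.
- One descriptor against conventional: 3.26/√2 = 2.30, power 63% at 228. At 250: 2.41, power 67%. N for 90% is 228 × 2 = 456.

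These losses depend only on the weights; SD and ICC cancel.

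**Other readings, each calibrated to 90% at 228 in the pessimistic scenario.**

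| Reading of the sizing run | One descriptor vs conventional | Combined vs conventional |
|---|---|---|
| 1-df, two versus two, conventional = own brand | 63% | 75% |
| 3-df condition-by-gender test (returns 42/68/228 or 40/66/228) | about 76% | about 87% |
| Only two conditions entered (returns 40/68/228) | 90% | not applicable |
| Input effect already halved by own brand, tested effect 2δ | over 99% | over 99% |

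**Unhalved effect.** For one descriptor at 228, noncentrality is 4.11/√(4 × 30.25/228) = 4.11/0.7285 = 5.64, power over 99%.

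**Own brand in the planned tests.** In Aim 3 items 11 and 12 own brand drops out: (4 − 1) − (2 − 1) = 4 − 2, and likewise for the other terms. Under H2.1 and H2.2, let the NAS versus non-NAS difference be D relative to conventional and 0 relative to own brand. The grouped contrast is then (D + 0)/2 = D/2, which is not the quantity that either Aim 2 interval estimates.

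**The case against.** The pilot, as the Compensation section describes it, covered conventional and organic descriptors only. The slashed label may simply map the new conditions onto two pilot ones, in which case the powered and tested contrasts match and 90% stands. Aims 2 and 3 are secondary, and Aim 1 has its own figure of 120. The extension to Aim 2 is hedged and gives a reason. The section's closing claim concerns an effect similar to the pilot's, and at the unhalved effect 228 is ample.

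Much of this stands, and it limits the point. A reader might infer that moderation power is really 63%. The documents do not support that: the figure needs the pessimistic scenario, a literal 1-df four-condition contrast, and equal conventional and own-brand means. The last condition is the one Aim 2 expects to fail in NAS smokers, and its failure can raise the power of the tested contrast as well as lower it. A reader might also infer that every Aim 2 and Aim 3 test is a descriptor-minus-conventional pair compared between groups. That is too broad, since Aim 2 also has own-brand pairs and H2.3 and H2.4 are within NAS smokers.

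The objection does not remove the mismatch. On every reading the section needs correcting, whether in the contrast, its label or the undisclosed inputs. The pessimistic scenario is also the one the plan chose for setting enrolment, because the pilot had only 22 subjects.

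**Conclusion.** The point holds as a mismatch between the powered and the tested contrasts. It is not an arithmetic error. The 90% at 228 is attached to a grouping that no planned interval uses, and the reason for extending it to Aim 2 does not address the different pattern hypothesised there.

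The true power cannot be fixed from the documents. In the pessimistic scenario at 228 the readings run from about 63% to over 99% for one descriptor against conventional, and from about 75% to over 99% for the two combined. All rest on a back-solved effect, equal groups, compound symmetry and a two-sided 5% test. At the unhalved effect there is no practical shortfall. It would be wrong to conclude that the trial is shown to be underpowered or that the primary Aim 1 comparisons are affected.

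**What to change.** In Sample size calculations:

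- Re-run the calculation for women versus men on organic − conventional and natural − conventional, separately and combined. State the means and contrast weights entered, and give the power at 228 and 250 in place of the grouped figure. If the original run used only two conditions, correct the label.
- Replace the sentence extending the Aim 3 number to Aim 2 with power for the Aim 2 contrasts under the hypothesised pattern: between NAS groups for H2.1 and H2.2 (against conventional and against own brand), and within NAS smokers for H2.3 and H2.4. Otherwise delete it.

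The cost is a software re-run and some restated figures. Enrolment does not change. The stated power may become less favourable.

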H(1.4), H(2.4), H(3.4): Biomarkers of exposure (Salivary aldehydes)

Concentrations of formaldehyde and acetaldehyde will be used as the outcome (difference between pre- and post-visit), where Normality is expected to be an appropriate assumption for the error term. However, just as with the other outcomes, if Normality does not

seem like an appropriate assumption, a transformed outcome (e.g. log-transformation) will first be explored, and if normality still does not hold, then we will consider a binary outcome using a median cutoff and use the logit link function so that the form of the best model will resemble a mixed effects logistic regression model (like above for the expectancies outcome); other link functions (e.g. probit) will be considered if model fit is a concern.

Hypothesis testing

H(1.1 - 1.4) are primary, and under the null hypotheses in H(1.1 - 1.4), the natural and organic condition means are equal to the conventional condition means. To test the hypotheses in Aim 1, we will first determine if the effects of the condition depend on gender and NAS-smoking status (as hypothesized in H(2.1) - H(3.4)). If the effect of the condition does not depend on gender or NAS-smoking status, then we will estimate the following effects in our model:

1. effect of the conventional condition
2. effect of the natural condition
3. effect of the organic condition

The null hypotheses in H(1.1 - 1.4) state that the conventional condition is equivalent to the natural and organic conditions. We can therefore test H(1.1 - 1.4) by estimating 95% credible intervals for the difference between the effects of the organic and natural conditions and the conventional condition. This will yield two credible intervals (one for the difference between natural and conventional effects, and another for the difference between organic and conventional effects) for each outcome (four outcomes) therefore making 8 total credible intervals of interest in Aim 1. If the effects of the condition depend on NAS-smoking status but do not depend on gender, then we will estimate the following effects in our model:

1. effect of the own brand condition for Non-NAS smokers
2. effect of the conventional condition for Non-NAS smokers
3. effect of the natural condition for Non-NAS smokers
4. effect of the organic condition for Non-NAS smokers
5. effect of the own brand condition for NAS smokers
6. effect of the conventional condition for NAS smokers

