Lastly, if the effects of the condition depend on both gender and NAS-smoking status (as hypothesized), then we will estimate 95% credible intervals for the differences between the conventional condition and the natural and organic conditions separately for non-NAS men, non-NAS women, NAS men, and NAS women. This will yield eight credible intervals for each outcome, so that there are 32 credible intervals of interest (four outcomes each with eight credible intervals) in Aim 1. If it is determined that the natural and organic condition effects can be combined into a single effect (e.g. if the Bayes factor provides evidence for the model that combines the effect over the model that includes separate effects for the natural and organic conditions), then only a single comparison will be made (rather than two comparisons) for the organic/natural conditions in above.

The multilevel modeling approach of Gelman et al. (2012)⁵² will be used to account for multiple comparisons within each aim. The number of comparisons (or contrasts of interest) in Aim 1 (which are based on the following contrasts: organic - conventional and natural - conventional) are determined according to whether the effect of the condition depends on NAS-smoking status or gender, and whether the effects for the natural and organic conditions can be combined (as outlined above). It is relatively straightforward to account for multiplicity within each outcome following the multilevel modeling approach outlined in Gelman et al. (2012).⁵² However, incorporating this approach across the four different outcomes in each aim may not be as trivial; the approach of Westfall (1997)⁵³ may instead be used to account for multiple outcomes.

To test H(2.1) and H(2.2), we will estimate effects for the following subgroups:

1. effect of NAS smokers under the own brand condition
2. effect of NAS smokers under the conventional condition
3. effect of NAS smokers under the natural condition
4. effect of NAS smokers under the organic condition
5. effect of non-NAS smokers under the own brand condition
6. effect non-NAS smokers under the conventional condition
7. effect non-NAS smokers under the natural condition
8. effect of non-NAS smokers under the organic condition

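### The statement that Aim 1 needs fewer subjects (120 for 90% power) holds only for the puff volume contrast pooled over all participants, not for the four-cell tests the plan hypothesizes

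*Combined protocol and SAP*

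**What the plan says.** **Sample size calculations.** For the gender-by-condition interaction (Aim 3), the plan needs 40 subjects for 90% power at the pilot values, and 228 when the effect is halved and the covariance matrix raised by half. It then says "Fewer subjects are needed to detect differences hypothesized in Aim 1 at each given power". The example is total puff volume, "which assumes a mean difference of 120ml with standard deviation 165ml", and the result is that "120 subjects are needed to achieve 90% power under an effect size that is 50% smaller" with the covariance again raised by half. The target of 228 completers follows. No Aim 1 calculation is shown for expectancies, chemical aftertaste or aldehydes.

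**Statistical analyses.** The primary comparisons are described as within-person differences by condition, averaged. The first candidate model listed lets the condition effect vary with both NAS status and gender, and is marked as the hypothesized one.

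**Hypothesis testing.** If neither moderator is retained, "We can therefore test H(1.1 - 1.4) by estimating 95% credible intervals for the difference" between each descriptor and conventional, giving 8 intervals over the four outcomes. If one is retained, the contrasts are tested within each group (16 intervals). The last case applies "if the effects of the condition depend on both gender and NAS-smoking status (as hypothesized"): the contrasts are then estimated separately in non-NAS men, non-NAS women, NAS men and NAS women, giving 32 intervals, all counted under Aim 1. If a Bayes factor supports it, natural and organic are merged and the number of contrasts halves.

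**The concern.** The sample size statement is unqualified: it covers every Aim 1 difference at every power level. Its only supporting calculation is one contrast in one undivided sample. The analysis section expects to divide that sample by four before testing Aim 1. Dividing the sample raises the total needed for a given power within each part, so the ordering of Aim 1 below Aim 3 cannot be carried over to the divided tests without a check.

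Aim 1 is the primary aim. A reader who takes the sentence at face value will assume ample power for whichever Aim 1 tests are reported, and will give an inconclusive cell-level interval more weight against an effect than the design supports.

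**Working it through.** **Inputs**
- Pilot topography: mean difference 120 ml, SD 165 ml (Sample size calculations).
- Conservative scenario: effect 120/2 = 60 ml; variance × 1.5, so SD = 165 × √1.5 = 202.1 ml.
- Correlation between repeated measures 0.5 (stated for the interaction calculation). At 0.5 the SD of a within-person difference equals the single-measure SD, so 202.1 ml applies whichever of the two the 165 ml is.
- 5% significance. Sidedness is not stated; I take two-sided, to match the 95% credible intervals.
- 228 completers. Equal brand groups and the goal of 50% women (Recruitment) give 228/2 = 114 per group and 228/4 = 57 per cell.

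**Reproducing the 120.** For one within-person contrast, n = [SD × (z₀.₉₇₅ + z₀.₉₀)/δ]² = [202.1 × (1.960 + 1.282)/60]² = 119.2, so 120. With the noncentral t, n = 120 gives 89.7% power and 122 is the first n above 90%. Variants miss: one-sided gives 98, multiplying the SD rather than the variance by 1.5 gives 179, and a two-sample comparison gives 239 per arm. So 120 is a single contrast over everyone, with no subgroup term.

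**Same inputs, divided sample.** Power is from the noncentral t with n − 1 degrees of freedom and noncentrality δ√n/SD; for example, 60 × √57/202.1 = 2.24 at n = 57. If natural and organic are merged, the contrast is their mean minus conventional, with variance SD² × 1.5 × (1 − ρ). At ρ = 0.5 that is 0.75 × SD², so the SD is 175.0 ml.

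| Aim 1 branch | n per test | Power, separate contrasts | Power, merged | Total for 90% in each part, separate | Merged |
|---|---|---|---|---|---|
| No moderator | 228 | 99.4% | 99.9% | 122 | 92 |
| One moderator | 114 | 88.2% | 95.2% | 2 × 122 = 244 | 2 × 92 = 184 |
| Two moderators | 57 | 59.6% | 72.0% | 4 × 122 = 488 | 4 × 92 = 368 |

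Against the 228 for Aim 3, Aim 1 needs fewer subjects in the first row, slightly more in the second (fewer if merged), and clearly more in the third.

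**Sensitivity of the four-cell figure (separate contrasts)**
- All 250 analysed (62 to 63 per cell): 63% to 64%.
- Cell effect other than 60 ml at n = 57: about 20% at 30 ml and 91% at 90 ml.
- Unreduced pilot values (120 ml, SD 165 ml) at n = 57: above 99%. The ordering still fails there: 22 per cell is 4 × 22 = 88 in total, against the plan's 40 for the interaction.

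**The case against.** The strongest reply is that the sentence is true of what it names. H1.1 to H1.4 are written without moderators, and the Statistical analyses section defines the primary comparisons as averages. For that contrast 120 is below 228, power at 228 is 99%, and nothing has been miscalculated. This stands, and it is why the point concerns the scope of a statement and not an arithmetic error. It does not settle the matter, because the Hypothesis testing section replaces the average with group or cell contrasts once a moderator is retained, and still counts them as Aim 1.

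Further replies stand in part:
- The one-moderator gap is trivial: 88% at 114 per group, 91% at 125, 95% at 114 if merged.
- Cells are used only when effects are judged to differ between them, so no single cell power exists; 60% is a reference value for a 60 ml effect.
- The planned multilevel model borrows strength and covariates reduce noise, so separate paired t tests are an approximation and exact power needs simulation. The sample size section gives no such calculation.
- The plan's closing claim of adequacy is for an effect like the pilot's, where cell power exceeds 99%. The conservative scenario nevertheless produced both the 120 and the 228.
- The remark that the calculations are usable because "they correspond to the model that is believed to be most likely true" justifies a non-Bayesian calculation. It does not promise that every figure uses the four-cell model, and the point does not rest on it.

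A reader might infer that each primary test has a 40% chance of missing a real effect, or that all four cells must be positive. The first holds only under the equal-effect, unmerged conditions above. No section requires the second.

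**Conclusion.** The unqualified sentence is correct for the pooled total puff volume contrast and incorrect for the branch the plan hypothesizes. There, in the conservative scenario, power is about 60% per cell (about 72% if natural and organic are merged), and 90% in each cell would take about 488 subjects (368 if merged) against 228. These figures assume two-sided 5%, correlation 0.5, 228 completers split evenly, 60 ml in every cell, and no multiplicity adjustment.

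It might be inferred that the trial is too small for its primary aim, or that the shortfall exists however moderation is resolved. The documents support neither. With no moderator retained the plan's statement is right, with one the gap is small or absent, and at the pilot effect every cell is well powered. What is missing is a statement of which Aim 1 test the 120 belongs to, and of the power of the others.

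**What to change.** Either of two changes resolves it.

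1. In the sample size section, limit the sentence and the 120 to the total puff volume contrast pooled over all participants. Add the approximate power at 228 completers in the conservative scenario: 99% pooled, 88% per group with one moderator (95% if merged), 60% per cell with two (72% if merged). State the conditions: equal 60 ml effects, even split, correlation 0.5, two-sided 5%, before multiplicity adjustment, paired-t approximation to the multilevel model.
2. In the Hypothesis testing section, define the Aim 1 primary test as the descriptor-minus-conventional contrast averaged over the NAS and gender cells, in line with the Statistical analyses section, and keep cell-level contrasts for Aims 2 and 3. The 120 then stands for topography.

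The first costs wording only and makes the stated Aim 1 power less favourable for the split analyses. The second changes the definition of the primary test, so it should be made before outcome data are examined. Neither changes enrolment. A simulation of the planned model would replace the approximate figures but is not needed for the correction.
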